12.6 Handling of Missing, Unused, and Spurious Data

12.6.1 Missing Date of Investigational Product

When the date of the last dose of investigational product is missing for a subject in the safety set, all efforts should be made to obtain the date from the investigator. If it is still missing after all efforts, then the last visit date will be used in the calculation of treatment duration.

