- a Dosing must occur on Day 1, on the same day as randomization. The duration of subject participation in this trial may be variable. In Part 1, subjects may receive open-label treatment through Day 7 or resolution of ARDS (whichever occurs earlier). A DMC will review safety data from Part 1 and determine whether Part 2 can be initiated and whether Part 2 treatment can be extended beyond Day 7. Required criteria for initiation of Part 2 will include (1) no fatal/life-threatening SAEs thought possibly related to APL-9 by the DMC, and (2) no more than 1 subject requiring premature treatment discontinuation by the investigator due to AEs or abnormal laboratory tests. In Part 2, dosing may be extended only in subjects who still require respiratory support (oxygen supplementation or mechanical ventilation) at Day 7 with an improved PaO2/FiO2 ratio of at least 20 mm Hg from baseline if ABG test results are available for comparison. If ABG test results are not available, an improvement of FiO2 of at least 4% in nonventilated subjects (eg, those on nasal cannula) and 10% in mechanically ventilated subjects is needed. FiO2 should be weaned following the site's protocol to keep oxygen saturation at 89% or above. Treatment beyond Day 7 and through any DMC-approved extension will be at the discretion of the investigator. In Part 2, subjects will receive treatment up to and including the DMC-approved treatment duration, discontinuation of respiratory support (oxygen supplementation or mechanical ventilation), or hospital discharge (whichever occurs latest). Through Part 2, the DMC may review efficacy and safety data and recommend changes to the study conduct on an ongoing basis, but it will be required to review efficacy and safety data after the 10th and 30th subjects reach the DMC-approved treatment duration, discontinuation of respiratory support, or hospital discharge (whichever occurs latest). Enrollment will not be suspended during the DMC reviews. Subjects who reach the end of the approved treatment duration, discontinuation of respiratory support, or hospital discharge (whichever occurs latest) must be assessed as indicated in the EOT and discharge day column (for example, a subject who reaches the end of the approved treatment and achieves discontinuation of respiratory support on Day 6 should be evaluated with a radiograph or CT scan even though it is not indicated as a Day 6 assessment). All subjects will be followed up at the safety follow-up assessment 30 days after last study treatment (up to and including Study Day 51 with a +7-day window), either in person (for subjects still hospitalized) or by phone (for subjects who have been discharged).

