## 10. DISCONTINUATION OF STUDY INTERVENTION AND SUBJECT DISCONTINUATION/WITHDRAWAL

#### **10.1.** Discontinuation of Study Intervention

Treatment with study drug (APL-9 IV or matching vehicle IV infusion) will terminate as follows:

- Part 1: at Day 7 or until or resolution of ARDS (PaO2/FiO2 ratio >300 mm Hg), whichever occurs earlier
- Part 2: at Day 7 or up to and including the approved treatment duration, discontinuation of respiratory support (supplemental oxygen or mechanical ventilation), or hospital discharge, whichever occurs latest

In Part 2, the DMC may decide to allow treatment with study drug beyond Day 7. If allowed by the DMC, study drug infusions can be extended at the discretion of the investigator beyond Day 7 up to and including Day 21. In Part 2, dosing may be extended only in subjects who still require respiratory support (oxygen supplementation or mechanical ventilation) at Day 7 with a PaO2/FiO2 ratio improved by at least 20 mm Hg from baseline if ABG test results are available for comparison. If ABG test results are not available, an improvement of FiO2 of at least 4% in nonventilated patients (eg, those on nasal cannula) and 10% in mechanically ventilated patients is needed. FiO2 should be weaned following the site's protocol to keep oxygen saturation at 89% or above. Treatment beyond Day 7 and up to and including any DMC-approved extension will be at the discretion of the investigator. However, study drug administration must end at the DMC-allowed maximal time point or upon the subject's discharge from the hospital. The time of transfer and termination of study drug treatment must be recorded in the subject's medical records and eCRF. If treatment is interrupted for any reason for greater than 24 hours, treatment may not be resumed.

In rare instances, it may be necessary for a subject to permanently discontinue study treatment (definitive discontinuation). The date of and reason for treatment discontinuation must be determined by the investigator and recorded in the subject's medical record and on the appropriate eCRF. If it is determined that there was more than one reason for the discontinuation, each reason should be documented in the source document and the most clinically relevant reason, as determined by the investigator, should be entered on the eCRF (see also Section 10.2).

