Subjects may receive treatment beyond Day 7 if the DMC approves an extended treatment duration following the review of data from Part 1 or during the conduct of Part 2. The DMC may approve any extended treatment duration up to and including Day 21; extended treatment will be allowed

only in subjects who still require respiratory support (oxygen supplementation or mechanical ventilation) at Day 7 with an improved PaO2/FiO2 ratio of at least a 20mm Hg from baseline if arterial blood gas (ABG) test results are available for comparison. If ABG test results are not available, an improvement in FiO2 of at least 4% in nonventilated patients (eg, those on nasal cannula) and 10% in mechanically ventilated patients is needed. FiO2 should be weaned following the site's protocol to keep oxygen saturation at 89% or above. Treatment beyond Day 7 and up to and including any DMC-approved extension will be at the discretion of the investigator.

Follow-up safety assessments for each subject will be collected 30 days following the last dose of study treatment (up to and including Study Day 51 with a +7-day window). Safety assessments may be performed any time during the 30-day follow-up period at the investigator's discretion but are required 30 days after the last dose of study drug (up to and including Study Day 51 with +7day window). These assessments will be conducted via inpatient assessment (for subjects still hospitalized) or by telephone call (for subjects discharged).

The DMC will perform safety and efficacy data reviews on an ongoing basis during Part 2. Two reviews will be required in Part 2:

- After the 10th subject reaches the approved treatment duration, discontinuation of respiratory support (oxygen supplementation or mechanical ventilation), or hospital discharge, whichever occurs latest
- After the 30th subject reaches the approved treatment duration, discontinuation of respiratory support (oxygen supplementation or mechanical ventilation), or hospital discharge, whichever occurs latest

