5.6 Exposure to Study Drug

The following parameters will be calculated and presented for safety set:

- Duration of treatment (days) defined as (the start date of last infusion the start date of first infusion date + 1)
- Number of infusions received (1 infusion, 2 infusions, etc.)

Clinical Protocol APL9-COV-201

Apellis Pharmaceutical, Inc Statistical Analysis Plan V2.0

- Number of infusions completed
- Number of infusions interrupted
- Number and percentage of patients with any dose interruption
- Number and percentage of subjects with infusion related reaction

Details of study treatment exposure will be listed for safety set.

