12.4 Definition of Visit Windows

Data will be summarized and analyzed based on the list of visits specified in the schedule of assessments (SOA) of the protocol. All the post-baseline records will be assigned to an appropriate analysis visit using the rules below:

- For the post-baseline visits, the lower and the upper bound for the analysis visit windows
 are defined as the midpoints of the target date of the scheduled visits.
- If the date of assessment falls in between the lower bound and the upper bound for a visit
 as specified in the schedule of assessments of the protocol, then it will be assigned to that
 visit.
- If the interval separating 2 scheduled visits is an even number of days, the middle day will be included in the lower bound of the next visit.

• End of Treatment visit for subjects who discontinued the study early and unscheduled visits will be mapped to post-baseline scheduled visits if they fall in a scheduled visit window. If assessment result is available in the original post-baseline scheduled visit, then the record will be used in the analysis. If assessment from the original post-baseline scheduled visit is unavailable, then the assessment result mapped from unscheduled/end of treatment visit will be used for analysis. If there are more than one unscheduled/end of treatment visits mapped to the same window, the one closer to the target day will be used for analysis. If more than one visits have the equal distance to the target day, then the earlier one will be used for analysis. If more than one visits on the same day, the time or the sequence number will be used to select the earlier record. If more than one visits on the same day and could not be differentiated by the time or the sequence number, mean value will be used for analysis.

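### A last-dose date that stays missing is replaced by an undefined last visit date, which for a study completer would add 30 to 37 days to reported treatment duration

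*SAP*

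**What the plan says.** SAP 12.6.1 applies to a safety-set subject whose date of last dose is missing. It first asks for a query ("all efforts should be made to obtain the date from the investigator"). If that fails, "then the last visit date will be used in the calculation of treatment duration". Nothing in the section defines that visit or limits the resulting date.

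SAP 5.6 measures treatment duration from the start date of the first infusion to the start date of the last, counting both days.

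On which visits exist, SAP 12.4 says: "Data will be summarized and analyzed based on the list of visits specified in the schedule of assessments (SOA) of the protocol". The last column of that schedule (Protocol Table 1) is the safety follow-up. SAP 3.1 says that the follow-up safety assessments "are required 30 days after the last dose of study drug", with a +7-day window, and footnote a to Table 1 extends this to all subjects. Protocol 10.3 calls a missed safety follow-up a missed visit, and Protocol 7.4 makes obtainable follow-up assessments part of completing the study.

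On the length of dosing, Protocol 7.1 lets the DMC approve treatment to Day 21 at most. Protocol 9.1.1 forbids dosing beyond the approved window, and Protocol 10.1 adds that "study drug administration must end at the DMC-allowed maximal time point or upon the subject's discharge from the hospital".

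**The concern.** The safety follow-up is scheduled by counting forward from the last dose. If its date stands in for the last dose, the whole follow-up interval is counted as treatment, however long the subject was really treated. The result is a duration that the protocol does not allow, since dosing is over by then and discharged subjects are contacted by telephone.

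What is at stake is the exposure table. Safety is the primary objective, and this table tells the reader how much treatment lies behind the adverse-event counts. An affected subject would appear to have been infused well past the approved limit. On this reading the error can only lengthen exposure.

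**Working it through.** **Inputs**
- First infusion on Day 1 (Protocol 11 defines Day 1 as the day of first administration).
- Safety follow-up at last dose + 30 days, window +7 (SAP 3.1; Protocol Table 1, footnote a).
- Duration = day of last infusion start − day of first infusion start + 1 (SAP 5.6).
- Longest approvable treatment: Day 21 (Protocol 7.1).
- About 30 subjects per arm (SAP 3.2).

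**The plan's own figure.** Latest follow-up day = 21 + 30 = 51, and 51 + 7 = 58. This reproduces the stated Study Day 51 with a +7-day window.

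**Duration when the follow-up date is imputed.** With last dose on day L, the true duration is L − 1 + 1 = L. The imputed duration runs from (L + 30) − 1 + 1 = L + 30 to (L + 37) − 1 + 1 = L + 37.

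| Last dose (day) | True duration (days) | Imputed duration (days) |
|---|---|---|
| 1 | 1 | 31 to 38 |
| 3 | 3 | 33 to 40 |
| 7 | 7 | 37 to 44 |
| 14 | 14 | 44 to 51 |
| 21 | 21 | 51 to 58 |

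The overstatement is 30 to 37 days in every row. The smallest possible imputed value, 31 days, already exceeds 21.

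**Effect on an arm.** Take 30 subjects, all truly treated for 7 days, one of them imputed:
- lower: (29 × 7 + 37)/30 = 240/30 = 8.0 days, or +14% (1.0/7);
- upper: (29 × 7 + 44)/30 = 247/30 = 8.23 days, or +18% (1.23/7).

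Each further affected subject adds 30/30 = 1.0 to 37/30 = 1.23 days to the mean. The reported maximum becomes 37 to 44 days.

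**How often.** The documents give no expected number of missing dates. With k affected subjects in an arm of 30, the mean rises by 1.0k to 1.23k days; with k = 0 nothing changes.

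**The case against.** The strongest reply is that the rule will hardly ever be used. Dosing is a supervised inpatient infusion. Protocol 9.4 has the date, time and duration of each dose entered in the eCRF, Protocol 10.1 requires the time of termination to be recorded, and SAP 12.6.1 acts only after a query has failed. This stands. It limits how often the error occurs, but not its size when it does.

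Second, the sponsor may have meant the end-of-treatment visit. The protocol mostly calls the 30-day contact an assessment, and SAP 12.6.2 to 12.6.4 use a different term, last study date, for the end of a subject's data. If the end-of-treatment visit on the last day of treatment was intended, the error is zero. This is possible, but the text does not say it, and Protocol 10.3 does call the follow-up a visit. The term needs defining either way.

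Third, the exposure summary also gives median and quartiles (SAP 12.1), which one outlier in 30 barely moves, and exposure is listed by subject, so an impossible value would be noticed. This also stands.

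A reader might infer two larger harms that the documents do not support:
- **A shifted TEAE window.** SAP 12.6.1 limits the imputed date to treatment duration. Even if it were reused in SAP 7.1, Protocol 11.2.5 ends adverse-event collection at the safety follow-up, so a later window would add essentially no collected events.
- **Flattered tolerability per day treated.** SAP 7.1 reports numbers and percentages of subjects and plans no exposure-adjusted rate. The missing date could also fall in either arm.

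**Conclusion.** The point holds as a defect in a fallback rule for a descriptive table. For a study completer whose last-dose date cannot be recovered, the rule as written overstates treatment duration by 30 to 37 days and always gives a value above the Day 21 maximum. One such subject in 30 raises a 7-day arm mean by 14% to 18% and sets the maximum. TEAE and SAE incidence, the efficacy endpoints and the tests are unaffected.

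This rests on two assumptions: that the last visit means the last scheduled visit attended, and that the subject reached the safety follow-up. It would be wrong to conclude that most subjects are affected. The rule touches only those with an unresolved date, and subjects who die, withdraw or are lost before follow-up have an earlier last visit and a smaller error.

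**What to change.** In SAP 12.6.1, replace the last visit date with the start date of the last infusion recorded in the eCRF, which is the quantity SAP 5.6 already uses. If there is no usable infusion record, use the end-of-treatment visit date, no later than the date of hospital discharge or death. State that the safety follow-up date is never used. The limit at discharge or death is needed because the end-of-treatment date is not a perfect anchor: footnote n to Table 1 puts those assessments on the last day of treatment, while Protocol 11 puts them at end of treatment or discharge, whichever is later.

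The cost is one or two sentences in the SAP. Every date is already collected and no clinical rule changes.

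A cap at the approved treatment duration should wait. Protocol 7.1, 9.1.1 and the Part 2 bullet in 10.1 end dosing at the latest of several events, one of them hospital discharge. A later sentence in 10.1 says that dosing must end at the DMC-allowed maximum or at discharge, and 9.1.1 also bars dosing beyond the approved window. These passages must be reconciled separately before a cap can be written.

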12.6.2 Missing or Partial Dates for Medications

When determining prior or concomitant medications, partial start dates of prior and concomitant medications will be assumed to be the earliest possible date consistent with the partial date.

- Medication start dates with a missing day and non-missing month and year will be assumed
 to have occurred on the first day of the non-missing month, except for medications
 occurring in the same month and year as the first dose of investigational drug, in which
 case the start date will be the first dose date.
- Medication start dates with missing day and month and non-missing year will be assumed to have occurred on the first day of the non-missing year (i.e., 01 January).
- A missing medication start date will be coded as the first dose date.

- Medications that are not ongoing and have a medication stop date with a missing day and non-missing month and year will be assumed to have stopped on the last day of the nonmissing month, except for medications stop in the same month and year as the last study date, in which case the stop date will be the last study date.
- Medications that are not ongoing and have a medication stop date with missing day and
 month and non-missing year will be assumed to have stopped on the last day of the nonmissing year (i.e., 31 December), except for medications stop in the same year as the last
 study date, in which case the stop date will be the last study date.

Imputation of missing or partial dates for medications is used only to determine whether an event is prior or concomitant medication, data listings will present the missing or partial date as recorded in the eCRF.

12.6.3 Missing or Partial Dates for Procedures

For records with a missing or partial procedure date, the following steps will be employed to determine whether the procedure is prior or concomitant:

- Procedure start dates with a missing day and non-missing month and year will be assumed
 to have occurred on the first day of the non-missing month, except for procedures occurring
 in the same month and year as the first dose of study treatment, in which case the start date
 will be the first dose date.
- Procedure start dates with missing day and month and non-missing year will be assumed to have occurred on the first day of the non-missing year (i.e., 01 January).
- A missing procedure start date will be coded as the first dose date.
- Procedures that are not ongoing and have a procedure stop date with a missing day and non-missing month and year will be assumed to have stopped on the last day of the nonmissing month, except for procedure stop in the same month and year as the last study date, in which case the stop date will be the last study date.
- Procedures that are not ongoing and have a procedure stop date with missing day and month
 and non-missing year will be assumed to have stopped on the last day of the non-missing
 year (i.e., 31 December), except for procedure stop in the same year as the last study date,
 in which case the stop date will be the last study date.

Imputation of missing or partial dates for procedures is used only to determine whether a procedure is prior or concomitant procedure, data listings will present the missing or partial date as recorded in the eCRF.

12.6.4 Missing or Partial Dates for Adverse Events

When the date of the adverse event is missing or partial for a subject in the safety set, all efforts should be made to resolve the full date from the investigator. The following conventions will be used to impute partial dates for adverse events. Note that the imputed values outlined here may not

always provide the most conservative date. Under those circumstances, the imputed value may be replaced by a date that will lead to a more conservative analysis.

1. Start Dates

- If the year is unknown, then the date will not be imputed and will be assigned a missing value
- If the month is unknown, then: If the year matches the first dose date year, then impute the month and day of the first dose date. Otherwise, assign 'January'.
- If the day is unknown, then: If the month and year match the first dose date month and year, then impute the day of the first dose date. Otherwise, assign the first day of the month.

2. Stop Dates

- If the year is unknown, then the date will not be imputed and will be assigned a missing value.
- If the month is unknown, then assign 'December', except for the event stop in the same year as the last study date, in which case the stop date will be the last study date.
- If the day is unknown, then assign the last day of the month, except for the event stop in the same month and year as the last study date, in which case the stop date will be the last study date.

If the stop date is complete and the imputed start date is after the stop date, then the start date will be imputed using the stop date.

Imputation of missing or partial dates for adverse events is used only to determine whether an adverse event is treatment-emergent and calculation of duration of adverse events; data listings will present the missing or partial date as recorded in the eCRF.

12.6.5 Missing Severity Assessment for Adverse Events

- If severity is missing for an AE starting prior to the date of the first dose of investigational product, then a severity of "Mild" will be assigned.
- If the severity is missing for an AE starting on or after the date of the first dose of investigational product, then a severity of "Severe" will be assigned.

The imputed values for severity assessment will be used for incidence summaries, while the actual values recorded in the eCRF will be used in data listings.

12.6.6 Missing Relationship to Investigational Product for Adverse Events

If the relationship to investigational product is missing for an AE starting on or after the date of the first dose of investigational product, a causality of "Related" will be assigned.

12.6.7 Detectable Limits of Clinical Laboratory Variables

Lab results beyond the detectable limits will be reported as detectable limits for calculating descriptive statistics. Original values will be listed.

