# 7.3. Justification for Dose

A single bolus infusion of 180 mg of APL-9 followed by continuous infusion of 360 mg/day will be tested in this study. This will result in an initial dose of 540 mg of APL-9 in the first 24 hours of dosing (followed by 360 mg/day on all subsequent days). This dose and higher doses were well tolerated in a previous study in healthy volunteers and demonstrated comparable PK and complement inhibition to that in prior cynomolgus monkey studies. More detailed information can be found in the APL-9 Investigator's Brochure.

The purpose of this dosing scheme is to achieve rapid complement inhibition by APL-9 upon initiation of treatment, followed by a regimen selected to keep the complement system consistently suppressed for the duration of study drug administration. Discontinuation of dosing is expected to restore normal complement activity within 24 hours.

[figure not shown]

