7.2 Clinical Laboratory Data

The detailed lab parameter list is summarized in Table 2 (Page 47) of study protocol APL9-COV-201 amendment 3. Continuous laboratory parameters will be normalized by converting values in original units to values in SI units and classified as normal, abnormal low, or abnormal high on normal ranges supplied by the local laboratories and upon employing standardization.

Observed values and change from baseline of clinical laboratory data (serum chemistry, hematology, coagulation, complement activation and inflammation, and continuous urinalysis parameters) will be summarized at each analysis visit. Categorical laboratory data will also be tabulated by the number and percentage of patients of each category at each analysis visit.

Frequency of abnormal (out-of-range) laboratory values will be tabulated by analysis visit.

If lab values are beyond detectable limit, the detectable limits will be used for analysis. The original collected values will be presented in the listings.

Clinical laboratory data will be presented in listings. Out of range laboratory results with their corresponding changes from baseline will be listed in separate listings.

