8. PHARMACOKINETIC ANALYSIS

8.1 Drug Concentration

The observed values and changes from baseline of APL-9 concentrations will be summarized for pharmacokinetic (PK) set at each scheduled time point using descriptive statistics (including at least mean, SD, CV, Min, Max, Geometric Mean, and %CV). The number and percentage of subjects with a BLQ value will also be tabulated. The handling of BLQ in the summary table is described in Section 8.2.

Linear and log-linear individual concentration profile plots against the actual study visit will be produced by study part and treatment group.

Linear and log-linear mean concentration plots against the actual study visit will be generated by study part and treatment group. The number of subjects contributing to each mean value at a visit will be presented above the x-axis.

A listing of concentration data will be presented by study part and treatment group. The actual time, deviation, and percent deviation from nominal time will be listed.

All summaries and analyses of the pharmacokinetic data will be based on the PK set.

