8.2 Handling BLQ Values

APL-9 concentrations reported as below the limit of quantification (BLQ) will be taken as zero for linear plots, and equal to the lower limit of quantification (LLOQ) for semi-logarithmic plots. For the computation of descriptive statistics, BLQ will be taken as zero, except for the calculation of the geometric mean where the LLOQ will be used.

For the estimation of PK parameters, concentrations that are recorded as BLQ prior to the first quantifiable value will be set to 0. Concentrations that are recorded at the end of the sampling period (i.e. no further quantifiable concentrations) will be set to missing and will not be used for the estimation of parameter values. If a BLQ value falls between two quantifiable concentrations the value will be set equal to the LLOQ, unless its exclusion can be justified (e.g. implausibility given the profile observed and known PK properties).

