9. PHARMACODYNAMIC ANALYSIS

9.1 Pharmacodynamic Data

The pharmacodynamic (PD) endpoints will be evaluated using the PD Population.

Observed values, changes from baseline and percentage changes from baseline in PD endpoints will be summarized by study part and treatment group at each protocol specified time point using descriptive statistics. PD markers include the following:

- complement activation (C3, C3a, C4, C4a, Bb, C5a, TCC, and alternative complement pathway hemolytic activity [AH50]),
- coagulopathy (reticulocyte count, schistocytes, lactate dehydrogenase, D-dimer, ferritin, haptoglobin, fibrinogen),
- inflammatory cytokines (C-reactive protein, tumor necrosis factor α , IL-1 β , and IL-6).

Spaghetti plots for individual observed values and individual changes from baseline will be presented graphically. Actual sampling times will be used for the graphical presentation of individual data

Observed values, changes from baseline, and percentage changes from baseline will also be presented graphically by study part and treatment group. Nominal sampling times will be used for the display in plots.

PD parameters will be listed together with changes from baseline and percentage changes from baseline by study part and treatment group.

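### Where PD results fall below an assay limit, SAP 7.2 and 12.6.7 substitute the limit and SAP 9.1 does not count them, so APL-9's effect on those markers would be understated by an unknown amount

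*SAP*

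**What the plan says.** The substitution rule appears twice. SAP 12.6.7 has "Lab results beyond the detectable limits will be reported as detectable limits for calculating descriptive statistics", and SAP 7.2 has "If lab values are beyond detectable limit, the detectable limits will be used for analysis". It applies at both ends of the assay range. Unaltered results go to listings only: "Original values will be listed".

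The rule reaches the PD markers through SAP 7.2. That section takes its parameter list from Protocol Table 2, which contains AH50, Bb, C3a, C4a, C5a, TCC, TNFα, IL-1β and IL-6, and it names "hematology, coagulation, complement activation and inflammation, and continuous urinalysis parameters" among the data to be summarized.

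SAP 9.1 plans descriptive output: "Observed values, changes from baseline and percentage changes from baseline in PD endpoints will be summarized by study part and treatment group". It contains no detection-limit rule and no count of results beyond a limit.

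APL-9 concentration is treated differently. SAP 8.1 says "The number and percentage of subjects with a BLQ value will also be tabulated", and SAP 8.2 says "For the computation of descriptive statistics, BLQ will be taken as zero", with the quantification limit used only for the geometric mean and semi-log plots.

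On expected effect, Protocol 7.3 describes a regimen chosen to "keep the complement system consistently suppressed for the duration of study drug administration".

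**The concern.** For a marker that complement inhibition lowers, results below the limit would be expected mainly on APL-9. A result below the limit lies between zero and the limit, so inserting the limit is the most upward choice available. The APL-9 mean moves up, its spread narrows, and the gap to vehicle closes. In a fully censored arm, the reported percentage change depends only on the assay limit and the baselines, whatever the residual activity.

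Cytokines raise a related problem. If many values in both arms are undetectable, a real fall on APL-9 can largely disappear from the means, and wholly from the medians.

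PD is the trial's direct evidence that the drug inhibited complement, in about 30 subjects per arm. SAP 7.2 does tabulate out-of-range laboratory values, but against normal ranges, so that table is no substitute for a count at the assay limit.

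**Working it through.** **Plan figures.** The documents state no assay limit, no expected marker level and no calculation on this point, so there is nothing to reproduce. Every marker level and limit below is an assumption.

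**1. General bound.** With lower limit L and a share p of an arm's values below it, substitution raises that arm's mean by p × (L − mean of the censored values), which is at most p × L. The vehicle-minus-APL-9 difference shrinks by the APL-9 rise minus the vehicle rise.

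**2. Mean difference (simulated).** Assumed lognormal data: vehicle mean 100 with CV 30%, APL-9 CV 60%, with the limit and the APL-9 residual mean varied. No vehicle values were below the limit.

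| Limit | APL-9 residual | APL-9 below limit | True difference | Under the rule | Shrinkage |
|---|---|---|---|---|---|
| 5 | 20 | 1% | 79.9 | 79.9 | 0% |
| 2 | 1 | 94% | 98.9 | 97.9 | 1% |
| 5 | 5 | 61% | 94.9 | 93.8 | 1% |
| 10 | 5 | 94% | 94.9 | 89.7 | 5.5% |
| 20 | 10 | 94% | 89.9 | 79.5 | 12% |
| 30 | 5 | about 100% | 94.9 | 69.9 | 26% |
| 30 | 1 | 100% | 98.9 | 69.9 | 29% |

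In the row with limit 10 and residual 5, the shrinkage is (94.9 − 89.7)/94.9 = 5.5%. In that case the vehicle/APL-9 ratio falls from 20.0 to 9.8 and the APL-9 SD from 3.0 to 1.1. Substituting zero gives a difference of 99.1 and half the limit gives 94.4, so zero and the limit bracket the true 94.9. The APL-9 median moves only when more than half of its values are below the limit.

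**3. Percentage change with a fully censored arm.** Assume AH50 baseline B is lognormal with median 80 and log-SD 0.35. The mean of 1/B is exp(0.35²/2)/80 = 1.0632/80 = 0.01329. The mean percentage change for a constant post-dose value v is 100 × (0.01329 × v − 1).

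- True residual 1 to 3: −98.7% to −96.0%.
- Reported with a limit of 5, 10, 15 or 25: about −93%, −87%, −80% or −67%, the same for any residual below the limit.

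**4. Cytokine with values below the limit in both arms.** Assume log-SD 1 and a true APL-9/vehicle ratio of 0.5. On the log scale, with arm mean m and limit c, the mean after substitution is c × Φ(c − m) + m × [1 − Φ(c − m)] + φ(c − m). With half of vehicle values below the limit (c = 0), vehicle (m = 0) gives 0.3989 and APL-9 (m = ln 0.5 = −0.6931) gives 0.1446. The ratio is exp(0.1446 − 0.3989) = 0.78.

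| Vehicle below limit | Geometric mean ratio (true 0.5) | Excess below limit on APL-9 |
|---|---|---|
| 30% | 0.67 | 27 points |
| 50% | 0.78 | 26 points |
| 70% | 0.87 | 19 points |
| 80% | 0.92 | 14 points |

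From 50% upward both medians equal the limit and their ratio is 1.0. The proportion below the limit still separates the arms there, and that is the number the plan does not tabulate.

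**The case against.** The strongest reply is that this is conditional and of limited consequence. Protocol 7.3 states an aim; suppressed need not mean below the limit, and no document gives a limit against which to judge it. With a low limit little is lost: at 5 in the AH50 example, −93% is reported against a true −96% to −99%. PD is summarized descriptively with no planned test, and for a marker APL-9 lowers the bias runs against the drug, so it cannot create a false claim of target engagement. Substituting the limit is a prespecified convention, and the geometric ratios in step 4 are not planned outputs for PD markers. All of that stands.

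A reader might also infer that a floor would be invisible. The documents do not support that. SAP 12.1 requires SD, quartiles, minimum and maximum; SAP 9.1 adds individual plots and PD listings; SAP 7.2 and 12.6.7 keep original values in listings. A heavily floored arm would show a small SD and a minimum, first quartile and median all equal to one value. What is missing is a direct count.

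The reply does not explain why results below the limit are counted for drug concentration but not for the markers of its effect. Nor does it remove the known direction of the bias wherever APL-9 values do fall below the limit.

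**Conclusion.** The point holds in conditional form, as a cheap improvement. The rule, its reach to complement and inflammation markers through SAP 7.2, and the absence of a count in SAP 9.1 are all in the text. Wherever more APL-9 than vehicle values fall below a limit, the APL-9 mean is biased upward, its SD is too small and the mean difference is understated. Under the assumed levels the loss ran from 0% to 29% of the mean difference. It is negligible when the limit is small relative to the vehicle level, or when APL-9 values stay above the limit.

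Two stronger readings are tempting and unsupported. One is that the plan will in fact report suppressed complement as the assay floor; without assay limits, nobody can say for which markers this would happen. The other is that it threatens the trial's conclusions. The primary endpoint is safety and no PD hypothesis test is planned, so neither is touched.

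**What to change.** In SAP 9.1:

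- State the detection-limit rule for PD markers and give each assay's lower and upper limits.
- Tabulate the number and percentage of results below and above the limit by marker, visit and arm, as SAP 8.1 already does for APL-9 concentration. This is the essential part.
- Where a large share of either arm is at the limit, replace the mean, SD and mean percentage change with that proportion by arm, its between-arm difference and a 90% CI, together with the median and quartiles, shown as less than the limit where they fall there. Alternatively, keep the means and show their sensitivity to substituting zero, half the limit and the limit.

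I would not prescribe a censored-regression (Tobit) model, because its arm effect has no finite estimate when one arm is fully censored, as in step 3. A single fixed cut-off for heavy censoring would be arbitrary; judgement by marker is enough.

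The cost is SAP wording, an extra row per marker table and a second summary format for heavily censored markers. It needs no new subject data.
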